### 15.1.2 Sensitivity Analysis of Primary Efficacy Endpoint

Sensitivity analyses for the primary endpoint include:

- Sensitivity to analysis set  
The same analysis will use the per-protocol analysis set
- Sensitivity to missing data assumptions  
The same analysis will use LOCF imputation for subscore other than endoscopy of Mayo score. For missing endoscopy subscore, BOCF imputation will be used .

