5.8 Early Withdrawal

The definition of an early subject withdrawal from the study will be any subject who is randomized to double-blind medication and, for any reason, is withdrawn prior to completion of the Visit 5 procedures.

A subject may voluntarily discontinue participation in the study at any time. The investigator may also, at his/her discretion; discontinue the subject from participating in the study at any time. In addition, the investigator must make every effort to have the subject return to the clinic as soon as possible after discontinuation of study drug for an Early Withdrawal Visit. An Early Withdrawal Visit may occur at a regular scheduled clinic visit or between clinic visits. The following evaluations and procedures should be completed and recorded in the eCRF.

- Concomitant medication assessment
- AE/SAE assessment

- Physical examination (recorded in source documents only)
- Vital signs
- Collect and review electronic diary
- Collect used study medication (blinded study medication)
- Assess compliance with investigational drug
- 12-Lead ECG
- Laboratory assessments (including chemistry, haematology, and pregnancy test for females of childbearing potential and routine urinalysis)
- Call IVRS to report subject's early withdrawal from the study
- Endoscopy, Mayo score, 9-point modified Mayo score, and partial Mayo score, if feasible.

A subject that is withdrawn from the study after being randomised to treatment cannot be re-screened and subjects who are withdrawn from the study will not be replaced. If the subject withdraws from the study, and also withdraws consent for disclosure of future information, no further evaluations should be performed, and no additional data should be collected. The sponsor may retain and continue to use any data collected before.

Thyroid specific criteria:

Subjects with deranged TSH level (outside of normal range) only, but normal free T4 or free T3. Investigator can follow-up the subject with thyroid function test and assess clinically in 4 weeks.

Deranged TSH level, with associated deranged free T4 and/or free T3(outside of normal range), the investigator should assess subject's clinical condition and decide if the subject should be withdrawn.

Subject with signs and/or symptoms suggestive of hypothyroidism or hyperthyroidism should have laboratory thyroid function performed. If any of the thyroid parameters (TSH, free T4, or free T3) were outside of normal range, the subject is to be withdrawn.

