6. Vital signs include resting blood pressure, heart rate, and body temperature. It is advised to measure them before any procedures or questionnaires.
7. Adverse events and Serious Adverse Events to be collected from the start of the study drug (visit 2) until the Follow-Up contact. However, any serious adverse events will be recorded from the time of consent.
8. Investigator has the option to use PPD test, QuantiFERON Gold test or T-Spot for TB screening. Subjects who have previously receive BCG vaccination will be tested by QuantiFERON Gold test/or T-Spot test, and the result will determine the subject eligibility for participation.
9. Urine pregnancy test to be done in females of childbearing potential only

10. β -Human Chorionic Gonadotrophin(β -HCG) to be done in females of childbearing potential at screening visit, and only to be done if urine pregnancy test positive at other study visits.
11. Early withdrawal visit should be done within 2 weeks after last dose/decision of withdrawal.
12. Only to be conducted in the early withdrawn subjects.

15. FSH to confirm postmenopausal status at screening visit only.

6. Study Treatments

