## 6.4 UNSCHEDULED VISITS, RETESTS AND EARLY TERMINATION DATA

In general, for by-visit summaries, data recorded at the nominal visit will be presented. Unscheduled measurements will not be included in by-visit summaries but will contribute best/ worst case value where required .

In the case of a retest (same visit number assigned), the latest available measurement for that visit will be used for by-visit summaries.

Listings will include scheduled, unscheduled, retest and early discontinuation data.

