## 6.5 WINDOWING CONVENTIONS

No visit windowing will be performed in the statistics for this study.

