### 15.2.2 Missing Data for Secondary Efficacy Endpoints

For dichotomized endpoints, missing data will be imputed as non-completers considered failure; if a patient is missing one or more Mayo subscores at the visit where the endpoint is being assessed, the patient would be considered a treatment failure.

For continuous endpoints, missing data will be imputed by using LOCF approach for results other than endoscopy of Mayo score. For missing endoscopy subscore, BOCF approach will be used.

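### Read as written, the imputation rule replaces an observed early-withdrawal endoscopy with the baseline score in one sensitivity analysis and in the Week 8 Mayo change scores

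*SAP*

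**What the plan says.** **Collection.** Protocol 5.8 defines an early withdrawal as a randomized subject who "is withdrawn prior to completion of the Visit 5 procedures", that is, before Week 8 is complete. The procedures listed for the early-withdrawal visit include "Endoscopy, Mayo score, 9-point modified Mayo score, and partial Mayo score, if feasible". In the Time and Event Table (Protocol 5.12), the endoscopy, Mayo and 9-point modified Mayo rows of the Follow-up/EW column carry footnote 12: "Only to be conducted in the early withdrawn subjects". Endoscopy is scheduled at baseline, at Week 8 and at early withdrawal, and at no other time.

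**Imputation.** For the primary endpoint, the missing-data sensitivity analysis in SAP 15.1.2 reads "The same analysis will use LOCF imputation for subscore other than endoscopy of Mayo score", followed by "For missing endoscopy subscore, BOCF imputation will be used". For the continuous secondary endpoints, SAP 15.2.2 does the same: "For missing endoscopy subscore, BOCF approach will be" used. Protocol 9.3.4.3 names LOCF for the other subscores and gives no rule for endoscopy. SAP 3.3 does not list BOCF among the changes from the protocol.

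**Visits.** SAP 6.5 says "No visit windowing will be performed in the statistics for this study". SAP 6.4 bases by-visit summaries on nominal visits and, for withdrawal data, says "Listings will include scheduled, unscheduled, retest and early discontinuation data". SAP Appendix 1 shows Early Withdrawal as a visit of its own.

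**The concern.** A patient who leaves before Week 8 may have a colonoscopy on record from after treatment began. Nothing in the SAP moves that result to Week 8, and endoscopy is the one subscore kept out of LOCF. The Week 8 endoscopy is then missing and is filled from baseline. The composite adds symptoms carried forward from after treatment to mucosa scored before treatment, even where an observed endoscopy contradicts the filled value.

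Two results would be affected: the imputation-based sensitivity analysis of clinical response, and the ANCOVAs of Week 8 change in 9-point and total Mayo score. The first matters because the primary analysis counts every non-completer as a failure (NCF), whereas in this analysis a withdrawn patient can count as a responder. Reasons for leaving may differ between placebo and drug, so the errors need not cancel between arms.

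**Working it through.** **1. What the choice of BOCF does.** With endoscopy scheduled only at baseline, Week 8 and early withdrawal, take a patient with no Week 8 endoscopy:
- No early-withdrawal endoscopy: the last observation is the baseline one, so LOCF and BOCF give the same value.
- Early-withdrawal endoscopy present: LOCF would use it, and BOCF does not.

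Apart from unscheduled endoscopies, the only practical effect of BOCF over LOCF is therefore to set aside an observed early-withdrawal endoscopy.

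**2. Range of error in one patient's change score.** Let *b* be the baseline endoscopy subscore (2 or 3 by inclusion criterion 2) and *e* the early-withdrawal subscore (0 to 3). With the same symptom subscores in both versions, the imputed total minus the observed total is *b* − *e*.
- Most favourable error: 2 − 3 = −1 point.
- Most unfavourable error: 3 − 0 = +3 points.

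**3. Effect on responder status.** SAP 15.1 requires a fall of at least 2 points and at least 30%, plus a rectal bleeding fall of at least 1 or an absolute bleeding subscore of 0 or 1. Scores below are stool/bleeding/endoscopy. The cases assume that the symptoms recorded at early withdrawal are the ones carried forward, which the SAP does not state.

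| Baseline | At withdrawal | Result on observed endoscopy | Score under BOCF | Result under BOCF |
|---|---|---|---|---|
| 2/2/2 = 6 | 1/1/3 = 5 | fall 1, 1/6 = 17%: non-responder | 1/1/2 = 4 | fall 2, 2/6 = 33%, bleeding down 1: responder |
| 2/2/3 = 7 | 2/1/1 = 4 | fall 3, 3/7 = 43%, bleeding down 1: responder | 2/1/3 = 6 | fall 1, 1/7 = 14%: non-responder |

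Across all 23 eligible baseline patterns (total 5 to 9, endoscopy 2 or 3) and all withdrawal patterns:
- Worse mucosa is possible from the 10 baselines with endoscopy 2, giving 10 × 16 = 160 combinations. BOCF calls 48 of them responders and the observed score calls 25, so 48 − 25 = 23 are false responders.
- Better mucosa gives 10 × 16 × 2 + 13 × 16 × 3 = 944 combinations. Of these, 218 are responders on the observed score and non-responders under BOCF.

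These are counts of score patterns, not probabilities. They show only that both directions are possible.

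**4. How many patients.** The plan's own figure first: 140 evaluable with 8% dropout gives 140/0.92 = 152.2, in line with the stated 152, or 38 per arm. Expected dropouts are 0.08 × 152 ≈ 12, or about 3 per arm.
- One reclassified patient moves an arm's sensitivity response rate by 1/38 = 2.6 percentage points.
- All 3 reclassified in one arm would move it by 3/38 = 7.9 points.
- An arm's mean change would shift by at most 3 × 1/38 = 0.08 points too favourable, or 3 × 3/38 = 0.24 points too unfavourable.

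Each figure is a ceiling. The endoscopy is done only where feasible, it must differ from baseline, and reclassification also requires crossing the response threshold. The range is 0 to about 3 patients per arm.

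**The case against.** The strongest reply has five parts.

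*The SAP never says the early-withdrawal endoscopy is discarded.* This stands. The nominal-visit rule is worded for by-visit summaries, and the listings sentence describes listings rather than exclusions. The reading comes from putting Sections 6.4, 6.5, 15.1.2 and 15.2.2 together. Nor can one say that no output shows the value: the subscore shift table in SAP 15.2.1 names no visits and might display it.

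*NCF is also checked elsewhere.* This stands. A reader might infer that this is the only test of the missing-data assumption. SAP 3.3 and 5.4 do not support that: the per-protocol set was redefined to require Week 8 efficacy data, expressly to give observed results without NCF. That analysis is an observed-case check, and BOCF does not enter it.

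*BOCF is conservative.* This stands only in part. Improvement is hidden over a wider range than worsening, but the first worked case shows a withdrawn patient with worse mucosa becoming a responder. The opposite inference, that the rule systematically inflates response, is equally unsupported.

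*An early-withdrawal endoscopy is not a Week 8 value either.* True. It may fall at any time before Week 8 is completed, and up to two weeks after the last dose or the decision to withdraw. Using it is LOCF, with its own assumption. It is still an observation made after treatment began, which the baseline score is not.

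*It may be a local reading.* This stands, and the documents do not settle it. Protocol 1.4.1 describes the endoscopy subscore as centrally read, and Protocol 7.2.5 sends only baseline and Week 8 images for central reading.

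**Conclusion.** The concern holds as a limited defect in two imputation rules. Read as written, SAP 15.1.2 and 15.2.2 put a pre-treatment endoscopy in place of one observed after treatment began and combine it with carried-forward symptoms. The error per patient runs from 1 point too favourable to 3 points too unfavourable, and it can create or remove a response.

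The conclusion rests on the inference that an early-withdrawal endoscopy counts as missing at Week 8. The two worked cases also assume that early-withdrawal symptoms feed the LOCF; if Week 4 symptoms are used instead, similar reclassification can still occur. About 3 patients per arm is what planned dropout allows, not an estimate of how many are affected.

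The primary NCF analysis, the observed-case per-protocol analysis, the binary secondary endpoints and partial Mayo (which has no endoscopy component) are untouched. Nothing here bears on the sample size or on the validity of the primary test.

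**What to change.** In SAP 15.1.2 and 15.2.2:

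1. When an early-withdrawal endoscopy subscore was obtained, use it together with the symptom subscores from the same visit.
2. Use BOCF for endoscopy only when no post-baseline endoscopy exists.
3. State whether the early-withdrawal endoscopy is read centrally or locally. If only a local reading exists, flag it and keep the current BOCF version alongside as a comparison.

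Leave the primary NCF analysis as it is. If the sponsor always meant the early-withdrawal endoscopy to be used, the text still needs a sentence saying so.

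The cost is a short addition to two sections and a change to the imputation code, with no new visits. If a central reading is chosen, early-withdrawal images would have to be sent for it. The downside is that the early-withdrawal value is still carried forward to Week 8, and it may be a local reading set against a centrally read baseline.

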## 15.2 SECONDARY ENDPOINTS

The secondary endpoints are as follows:

- The percentage of patients with clinical remission (per 9-point modified Mayo score) at week 8;
- The percentage of patients with clinical remission (per total Mayo score) at week 8
- The percentage of patients achieve endoscopic remission at week 8
- Change from baseline in 9-point modified Mayo score at week 8
- Change from baseline in total Mayo score at week 8
- Changes from baseline in partial Mayo score (Mayo score without endoscopy) at week 1, 4, 8, 9, 12 and 16.

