1.4.2 Secondary Efficacy Endpoints

- The percentage of subjects that achieve clinical remission per 9-point modified Mayo score at week 8, where stool frequency subscore ≤ 1 , rectal bleeding subscore of 0, and endoscopic subscore ≤ 1
- The percentage of subjects that achieve clinical remission at week 8 as per total Mayo score of 2 points or lower than 2, with no individual subscore exceeding 1 point and a rectal bleeding subscore of 0.
- The percentage of subjects that achieve endoscopic remission (mucosal healing) at week 8, defined by Mayo endoscopic subscore ≤ 1 point.
- Change from baseline in 9 point modified Mayo score at week 8.
- Change from baseline in total Mayo score at week 8.
- Change from baseline in partial Mayo score (Mayo score without endoscopy) at week 1, 4, 8, 9, 12 and 16.
- Change from baseline in the level of biomarkers CRP, faecal calprotectin.
- The systemic exposure of SHR0302 in steady state in Ulcerative Colitis patients (i.e. concentration and area under the curve).

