7.3.7 Fecal Calprotectin

Fecal calprotectin is a 36kDa calcium and zinc binding protein which is neutrophil derived and it represents 60% of cytosolic proteins in granulocytes. It is considered as a measurement of neutrophil migration to the gastrointestinal tract. Fecal calprotectin is a very stable marker (stable for one week at room temperature). There is a growing body of evidence that fecal calprotectin correlates well with disease activity and making it a useful tool in monitoring disease and treatment (13). Fecal calprotectin measurement will be collected as detailed in [Section 5.12 – Time and Event table](#), from screening until the end of study visit (week 18) and will be analyzed by a central laboratory.

Subjects will be supplied with stool sample collection kits in advance and will be instructed to collect the sample at home, 1 day before the upcoming visit at which they have to provide the sample. Fecal samples (~20 g) for analysis of fecal calprotectin will be collected into the labeled stool collection containers, at protocol specified times (see [Section 5.12 – Time and Event table](#)) and shipped to central laboratory based on the laboratory manual. Samples will be analyzed using a validated analytical method.

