9.3.4.2 Missing Data

Binary data: Non-completers considered failure (NCF) will be used.

Continuous data: Last-observation-carried-forward (LOCF) approach will be used

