9.3.4.3 Efficacy Analysis

Analysis of the Primary Efficacy Endpoint

The primary analysis will be based on the FAS population. In addition, an analysis of the PPS population will be used to support the primary efficacy analysis.

For clinical response at week 8, the comparisons of the percentage of subjects achieving clinical response in each treatment versus placebo will be made using a stratified Cochran-Mantel-Haenszel (CMH) test with stratification according to prior anti- TNF α /biological treatment (with or without). Missing data will be imputed as Non-completers considered failure (NCF).

Sensitivity analyses for the primary endpoint include: (1) the same analysis using the per-protocol analysis set (2) using last-observation-carried-forward (LOCF) imputation for subscore other than endoscopy of Mayo score.

Analysis of the Secondary Efficacy Endpoints

Dichotomized secondary efficacy endpoints listed below will be analyzed by using a CMH Chi-Square test with stratification according to prior anti- TNF α treatment (with or without). Missing data will be imputed as Non-completers considered failure (NCF).

- ✓ The percentage of subjects with clinical remission (per 9-point modified Mayo score) at week 8
- ✓ The percentage of subjects with clinical remission (per total Mayo score) at week 8
- ✓ The percentage of subjects achieve endoscopic remission at week 8

The continuous secondary endpoints listed below will be analyzed using an analysis of covariance (ANCOVA) model including treatment group, baseline value, with/without previous exposure to anti-TNF α treatment as main effects. Missing data will be imputed by using Last-observation-carried-forward (LOCF) approach for subscore other than endoscopy of Mayo score.

- ✓ Change from baseline in 9-point modified Mayo score at week 8
- ✓ Change from baseline in total Mayo score at week 8
- ✓ Changes from baseline in partial Mayo score (Mayo score without endoscopy) at week 1, 4, 8, 9, 12 and 16.
- ✓ Change from baseline in the level of biomarkers CRP, fecal calprotectin.

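### SAP 15.2 and 15.2.1 leave out the protocol's ANCOVA for change from baseline in CRP and faecal calprotectin, and SAP 3.3 does not declare the departure

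*SAP*

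**What the plan says.** Protocol 1.4.2 lists "Change from baseline in the level of biomarkers CRP, faecal calprotectin" among the secondary efficacy endpoints, and protocol 7.2.2 repeats it. Protocol 9.3.4.3 sets the method: "The continuous secondary endpoints listed below will be analyzed using an analysis of covariance (ANCOVA) model including treatment group, baseline value", together with prior anti-TNFα exposure. The last item in the list under that sentence is "Change from baseline in the level of biomarkers CRP, fecal calprotectin".

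SAP 2.2 retains evaluation of the change in these two markers as a secondary objective. The SAP text names neither marker again. SAP 15.2 opens with "The secondary endpoints are as follows" and gives six endpoints, all derived from Mayo scores. SAP 15.2.1 places all secondary endpoint analyses on the FAS and describes ANCOVA for the 9-point modified, total and partial Mayo scores only.

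SAP 3.3, the section for departures from the protocol, records two changes: the added enrolled and randomized sets, and the redefined per-protocol set. SAP 1 states separately that pharmacokinetic analysis lies outside the document.

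**The concern.** The SAP is what the programmers follow. Followed as written, it drops a model-based comparison that the protocol promised for a secondary efficacy endpoint, while still claiming the objective that the comparison serves. Because SAP 3.3 is silent, a reader cannot tell a deliberate decision from an oversight.

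What is at stake is the placebo comparison for the trial's two laboratory markers of inflammation. SAP 3.1 says that anti-inflammatory data from this study, among other results, will inform which one or two doses go forward. The planned ANCOVA compares arms as randomized, adjusted for baseline and prior exposure. Without it, the SAP text offers at most unadjusted changes by visit for that decision.

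**Working it through.** The plan gives no figure on this point, so the check sets the texts side by side and counts endpoints.

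**Count of endpoints**

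- Protocol 1.4.2 and 7.2.2: 3 dichotomous + 3 Mayo changes + 1 biomarker change + 1 pharmacokinetic exposure = 8.
- SAP 15.2: 3 dichotomous + 3 Mayo changes = 6.
- Not carried over: 8 − 6 = 2, namely pharmacokinetics and the biomarkers.
- Protocol 9.3.4.3 assigns a test or model to 3 (CMH) + 4 (ANCOVA) = 7 endpoints. SAP 15.2.1 has a method for 6 of them. Within the ANCOVA list it covers 3 of 4, and the biomarker item is the one missing.

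**Was the omission declared?**

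| Endpoint not in SAP 15.2 | Declared? | Where |
|---|---|---|
| Pharmacokinetic exposure | Yes | SAP 1 |
| Change in CRP and faecal calprotectin | No | Not in SAP 1 or SAP 3.3 |

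**Could a protocol version difference explain it?** SAP 1 says that the SAP rests on protocol version 3.0. The later amendment reproduced in the protocol, No. 03, changes sections 5.3, 5.9 and 7.3.15. It does not touch 9.3.4.3, so the biomarker ANCOVA was not introduced by that amendment.

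**What the SAP text leaves for the markers.** SAP 16.3 covers central-laboratory data, including a category of other tests, and protocol Table 3 lists both markers in its column of other tests. The markers therefore seem to fall under SAP 16.3, although this is an inference because that section does not name them. The two routes differ as follows.

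| Feature | Protocol 9.3.4.3, with the FAS rule of SAP 15.2.1 | SAP 16.3 |
|---|---|---|
| Analysis set | FAS | Safety Set |
| Grouping | Randomized treatment | Treatment actually received |
| Method | ANCOVA adjusted for baseline and prior exposure | Observed values, changes and shifts by visit |
| Comparison with placebo | Yes | None: SAP 16 allows one only where the section specifies it, and 16.3 does not |

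**Can the protocol's model be run on planned data?** Yes. Table 1 of protocol 5.12 schedules CRP at baseline and Weeks 1, 4 and 8, and calprotectin at baseline and Weeks 4 and 8, all within the placebo-controlled phase. Neither document names the visit or visits at which the biomarker ANCOVA is to be evaluated.

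**The case against.** The best defence is that the markers are not ignored. SAP 16.3 promises actual values and changes by visit for all laboratory data, the protocol describes both markers within its safety assessments, and the objective in SAP 2.2 speaks only of evaluating change from baseline. On this view a descriptive summary meets the objective. The output templates cited in SAP 8 might also contain a biomarker ANCOVA table, and the protocol's model remains prespecified whatever the SAP says.

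Part of this stands. A reader might infer that the biomarkers would go unreported, or that the comparison has been abandoned for good. The documents do not show either: descriptive reporting is likely, and the templates are unseen. But protocol 9.3.4.3 promised more than description, SAP 16.3 neither uses the FAS nor compares arms, and a template would not supply the declaration missing from SAP 3.3.

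Three further readings go beyond the documents:

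- **Conflicting missing-data rules.** For continuous data, protocol 9.3.4.2 says "Last-observation-carried-forward (LOCF) approach will be used", without restriction. SAP 15.2.2 says, for continuous endpoints, that "missing data will be imputed by using LOCF approach for results other than endoscopy of Mayo score". Both read naturally as LOCF for laboratory values. Protocol 9.3.4.3 words its rule as an "approach for subscore other than endoscopy of Mayo score", but it offers no competing rule for biomarkers. A sentence of confirmation is enough.
- **A doubtful calprotectin baseline.** Protocol 7.3.7 describes collection from screening to Week 18, which might suggest a screening value that could serve as baseline. The same sentence refers to the Time and Event table, and that table has no screening sample for calprotectin.
- **Choices made after unblinding.** SAP 4.2 sends unblinded Week 8 outputs to a sponsor team while the programming team stays blinded. Nothing in the documents shows that unblinded staff would choose the biomarker visits, so this remains speculation.

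**Conclusion.** The point holds for the SAP text. One of the seven secondary endpoints to which the protocol assigns a test or model, covering two markers, has no corresponding method in the SAP, and the departure is undeclared. The SAP's own objective is left with no stated comparison against placebo.

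The consequence is limited. Hochberg control covers the primary endpoint only, so no confirmatory claim, sample size or error rate changes. No effect on an estimate can be sized, because the documents give no biomarker variability or expected difference. It should be corrected, but it does not threaten the trial.

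The conclusion rests on two assumptions: that both markers fall under the laboratory summaries of SAP 16.3, and that the unseen templates do not already restore the ANCOVA. If the templates do restore it, what remains is a gap in the SAP text and an inconsistency between the two.

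**What to change.** Add change from baseline in CRP and in faecal calprotectin to SAP 15.2 and 15.2.1:

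- Use the FAS and the protocol's ANCOVA.
- Name the analysis visits from Table 1. For the comparison with placebo these are Weeks 1, 4 and 8 for CRP and Weeks 4 and 8 for calprotectin.
- State that the LOCF rule of protocol 9.3.4.2 and SAP 15.2.2 applies to both markers.

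If the sponsor meant to drop the ANCOVA, enter that in SAP 3.3 with the reason, and say in SAP 16.3 that the markers will be summarized descriptively. In either case, check that the output templates agree.

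The cost is a short SAP amendment and a few tables. No new data are needed, because both markers are already scheduled at these visits.
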